## Subject Recruitment and Compensation

Participants may be recruited using 1) flyers and posters at Duke University Medical Center (DUMC) campus and the surrounding Research Triangle area, 2) online advertisements used on DukeHealth.org, DukeList, Craigslist, the UNC Psychiatry webpage <http://www.med.unc.edu/psych/research>, UNC's research site, Join the Conquest <https://jointheconquest.org/index.php/en/>, and facebook 3) direct referrals from local healthcare providers, Duke/UNC outpatient clinics, and other studies of depression 5) Our IRB-approved participant registry (IRB# Pro00000853) in the CB RTP, 6) Duke Clinical Research

Unit (DCRU) volunteer registry, 7) ResearchMatch.org, (see below for description of the CB RTP registry, DCRU volunteer registry, ResearchMatch.org).

The content of recruitment materials will be based on flyers, brochures and email/website scripts (see recruitment materials).

Prospective participants will either 1) contact the study coordinator's office at Duke or be called for a telephone screening interview, administered by a Study Coordinator/approved study team member, or 2) they may visit the websites ClinicalTrials.gov or Dukehealth.org and see the study description or posting. The telephone-screening instrument (see telephone script) is designed to rule out individuals who clearly meet certain exclusion criteria. The Duke study coordinator or approved study staff member will go through the telephone script document within Qualtrics & will be directly entering potential participant's responses to the telephone script electronically-thus no paper copies of the telephone script will exist. Because this study includes individuals with a range of psychiatric diagnoses, we expect most individuals will qualify at the phone screen for a face-to-face diagnostic assessment with the study Clinical Assessor to assess inclusion/exclusion criteria. If potential participants are ruled out via the phone script, their contact information will not be collected but all previous data collected prior to them ruling out will be kept in Qualtrics under a record number.

As an aid to shorten the recruitment prescreening process, prospective participants will be directed by all Duke flyers & brochures to the online screen survey within Duke's Qualtrics platform. Once on the Qualtrics online screen, they will read a description of the study (a modified version of the IRB approved phone screen) and if interested, will continue with answering the online screen questions (see online screen script for Qualtrics). The Qualtrics survey begins with an information statement designed to describe the study, risks and benefits in the absence of informed consent. If they agree to continue, they will then be asked their current age & if their age meets the study inclusion/exclusion criteria, they will continue on with the rest of the Qualtrics online screen as per Qualtrics online script. If they do not meet the age requirement, they will receive a message in Qualtrics indicating that they are not eligible and the survey will end. The results from the Qualtrics online survey will be monitored by the study coordinator and other study staff who will have access via a username and password. The data from the online survey can be imported to a SPSS or an excel .csv file which can only be accessed by the approved study team. Each day, study staff can check results of the online survey to see if any new potential participants have completed the survey and contact those people to either set up their first appointment or inform them that they don't qualify for the study per inclusion/exclusion criteria. Upon download of the prescreening information from Qualtrics by the study coordinator or designated study staff, if it is noted that the subject did not complete all of the online screen questions, the plan is for the study coordinator/staff to contact the subject. They would thank them for starting the screen and prompt them to complete the online screen again or by phone (if easier, using the phone script) if they are still possibly interested in the study.

If the potential participant is indeed ineligible for in-person screening, the study coordinator/approved study team member will log in to Qualtrics and remove their contact information from the study record by the end of the study enrollment period. After removing the contact information, the record number will continue to exist in Qualtrics with only the subject's research information. We estimate that across both study phases, approximately 150 online/phone screen interviews will be needed to enroll 90 subjects to get 72 who complete the study.

**CBRTP Database Registry:** Subjects who have previously agreed to be in our database registry (IRB# Pro00000853) to be considered for research studies would be contacted either to do a phone screen or directed to the Qualtrics online screen after reading through the phone script information to introduce the study and see if the individual is interested in being screened. Those interested participants will be given information from CBRTP staff about the study and scheduled for an appointment.

**DCRU Volunteer Registry:** This is a registry that the DCRU has that contains a list of potential study volunteers who have participated in research within the DCRU, who have said they would be interested in participating in other research. In exchange for a fee from our study team, a member of the DCRU team will identify potential research volunteers based on our study specific inclusion/exclusion that we give them and they will send out an email with a blurb about our study (this content is first approved by the IRB) and our contact information. Interested participants would then contact our study coordinator and complete a phone screen or go directly to the Qualtrics online screen for the study.

**ResearchMatch.org:** ResearchMatch.org is a national electronic, web-based recruitment tool that was created through the Clinical & Translational Science Awards Consortium in 2009 and is maintained at Vanderbilt University. There is no cost for researchers at participating institutions in the ResearchMatch Network to use ResearchMatch for the purposes of conducting recruitment feasibility analysis or participant recruitment. The Vanderbilt IRB provides oversight for ResearchMatch as a recruitment tool and this has been documented within the ResearchMatch IRB Letter of Understanding (available upon request). We would be sending a study recruitment message to potential study volunteers through ResearchMatch.org. ResearchMatch requires us to confirm that the recruitment language has been IRB approved and that our direct study contact information has been removed (email/phone/website) before sending our study announcement through ResearchMatch to volunteers that appear to be a good match for our study. The study PI, [name], will seek approval from the institutional liaison to have ResearchMatch recruitment access where he is able to search for appropriate matches amongst the non-identifiable ResearchMatch Volunteer profiles in the system. Our study's recruitment content will be inserted into the standard ResearchMatch electronic notification that informs possible matched Volunteers that we have identified them as a potential match for our study. The secure ResearchMatch clearinghouse will route this standard ResearchMatch notification that includes the IRB approved study content that we enter on "Contacting Volunteers" steps available through ResearchMatch (i.e. similar to the content available on a flyer or poster) to each of these ResearchMatch volunteers. These potential matching volunteers will have the option of replying yes, no, or not respond through a set of quick links available in this notification to our study announcement. By responding yes, the volunteer has

authorized ResearchMatch to release their contact information to us. This contact information of the Yes responding ResearchMatch Volunteers will be made available on our “Managing my Study” dashboard. Once we receive the contact information for those volunteers who respond yes, a member of our study staff would contact them to do a phone screen or direct them to our Qualtrics online screen after reading through the phone script information to introduce the study and see if the individual is interested in being screened.

Social Media: We plan to post ads for the study on social media websites such as Facebook. We will create a study facebook profile and place adds using the study page profile. The language in the ads will follow the language approved by the IRB for internet content. We may forward the link to the online adds from study staff personal Facebook accounts also.

Compensation. Compensation is as follows:

\$60 for individuals who are eligible and complete the full assessment

\$10 for those who are ruled out on the assessment day and complete only a partial assessment (approx 30 minutes)

\$75 after completion of assessment and training session

\$85 after completion of full study

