Our team's intervention that generalizes emotion regulation skills is a novel approach to testing if reducing emotional distress reduces emotion perception biases. To study the longitudinal effects of emotion regulation skills on emotion perception, these skills must be applied over time in patients' daily lives. In almost all behavioral therapies, the learning process occurs inside a clinic setting, and patients are expected to transfer this learning outside the clinic setting to the natural environment. However, patients often find it extremely difficult to generalize newly learned adaptive responses from one context to another (Stokes & Osnes, 2016). A key principle that can be used to facilitate generalization of newly learned behavior across contexts is: stimuli that are paired with training and transported into relevant contexts in the natural environment can be used as functional mediators to promote generalization. (Stokes & Osnes, 2016) This has been tested in our lab within adults with a variety of psychiatric diagnoses all characterized by having high difficulties with emotion regulation. Preliminary findings from our NIMH-funded study with emotionally dysregulated adults, "Evaluating a Novel Method of Generalizing Emotion Regulation" (IRB #: Pro000035922), demonstrated that within the lab, auditory reminders of habituation (i.e. natural reductions in emotional arousal over time) reduced emotional distress ( $F=6.75$ ,  $p=.011$ ) and arousal ( $F=7.05$ ,  $p=.009$ ) significantly more than a control condition. Emotional distress and arousal were assessed with both self-report (e.g. Subjective Units of Distress) and physiological measures (e.g. galvanic skin conductance). Reminders delivered via mobile phones over one week also significantly reduced emotional distress compared to placebo sounds ( $X^2=11.54$ ,  $p<.001$ ). These findings suggest promise for the use of novel reminders of learned emotion regulation skills to improve the ability to perceive other people's emotions in real social contexts. The next steps in this research program is to test the effects of this intervention on other psychological processes that are fundamental to daily functioning, such as emotion perception.

In sum, this study investigates the impact of a novel, generalizable emotion regulation micro-intervention on emotion perception biases in a transdiagnostic sample of adults. Negative biases in

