## Measures and Tasks

Interviews: During the intake session, diagnostic exclusions and current/past prevalence of Axis I and II diagnoses will be determined by the Structured Clinical Interview for Mental Disorders-I and II (SCID-I and II for DSM-5), interviews with demonstrated reliability used in our lab. The Treatment History Interview, brief version (B-THI; Linehan & Heard, 1987) will also be used at the intake session to assess previous and ongoing psychiatric services received and the NART will assess reading ability. All interviews will be videotaped or audio recorded and [name] will determine the reliability of every tenth interview. These video and/or audio recordings will be recorded directly onto the assessor's Duke computer, using a USB connected web camera that is connected to the hard drive of that computer. The recordings do contain PHI and thus the Duke lab computer used for recording has been encrypted with PGP. These video/audio files will be only temporarily stored on the local Duke computer and will be moved to Department of Psychiatry & Behavioral Sciences protected folder.

If the participant recently took part in another study at CBRTTP, he or she may not be required to complete all portions of the SCID interviews. Specifically, if the participant completed a SCID-I diagnostic interview with one of our study assessors within the previous four weeks, he or she would only be required to complete any portions of the SCID-I not completed as part of the earlier study assessment. If the participant completed the SCID-II within the previous six months, he or she would not be required to complete the SCID-II. In those cases, data from the earlier assessments would be used for this study. These procedures reduce the burden on the participant by eliminating the need to duplicate lengthy interviews, while still ensuring that the data is current.

Emotion Perception: The main outcome measure of emotion perception will be assessed with behavioral tasks, described below.

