Condition 1: Mindful Breathing. Participants assigned to this condition will first receive an orientation to mindful breathing, an emotion regulation skill based on Mindfulness Based Stress Reduction (Kabat-Zinn, 1990). The experimenter will orient them to the concept of focusing attention on the breath while feeling intense emotions, explaining that it's an active skill that one can use to calm down when distressed. After the initial orientation, participants are instructed to participate in the stressor task while practicing the mindful breathing skill. Reductions in emotional arousal will be continuously monitored using a real-time monitoring program that samples arousal through skin conductance every 500ms relative to the average baseline arousal. Emotional distress will also be assessed repeatedly throughout the task (SUDS). Once participants reduced their sympathetic arousal (returning to baseline in skin conductance) in the stressor task, a novel tone will be heard through the headphones. Through classical conditioning, participants learn to associate this specific sound with reductions in negative emotional arousal and distress.

Condition 2: Habituation. This comparison condition will most closely resemble the procedures of the previous study on generalizing emotion regulation (Pro00035922). Participants will hear each stressor for a minimum of 2 and a maximum of 4 times. Reductions in emotional arousal will be continuously monitored using a real-time monitoring program that samples arousal through skin conductance every 500ms relative to the average baseline arousal. Emotional distress will also be assessed repeatedly throughout the task (SUDS). Once participants reduced their sympathetic arousal (returning to baseline in skin conductance) in the stressor task, a novel tone will be heard through the headphones. Through classical conditioning, participants learn to associate this specific sound with reductions in negative emotional arousal and distress.

Condition 3: Control. This control condition will only present the stressor task without further instructions. Although emotional distress (SUDS) and sympathetic arousal (SCR) will be measured in this task as the first condition, participants in this condition will not hear the tones.

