## Selection of Subjects

Inclusion criteria include

- (1) ages 18-55;
- (2) have a smartphone and agree to receive text-messages;
- (3) high emotion dysregulation, assessed with the Difficulties with Emotion Regulation Scale (DERS)(Gratz & Roemer, 2004). There is no single consensus definition of difficulties with emotion regulation. However, one influential contemporary model proposes a multi-dimensional approach to conceptualizing difficulties with emotion regulation, including difficulties with: emotional awareness, emotional clarity, achieving goals when upset, impulsivity when upset, unwillingness to accept negative affect when upset, and accessing strategies to regulate emotions when upset (Gratz & Roemer, 2004). In the present application, we utilize this model and accompanying measure, the Difficulties with Emotion Regulation Scale (DERS; Gratz & Roemer), when characterizing our sample as being individuals who have problems regulating emotions. The mean DERS total score across all published reports (n = 13) with adult psychiatric samples (n = 19) is 112.15 (SD = 22.38). Following the established protocols from previous studies, we will use a total score of 90 or higher in the DERS for inclusion. In our previous study (Pro000035922), the 208 eligible participants had a mean DERS score of 117.6 (SD=17.95) at intake. These participants met criteria for a variety of affective and personality disorders, including major depression (68.3%, 22.1% current), generalized anxiety disorder (40.4%), and borderline personality disorder (11.1%). Therefore, we are confident that this DERS threshold will ensure recruitment of a transdiagnostic, clinical sample with emotion dysregulation.

Exclusion criteria include

- (1) Current mania;
- (2) Meets criteria for any current psychotic disorder symptom;
- (3) Currently/chronically homeless;
- (4) Current suicidal ideation (see data & safety section for specific criteria);
- (5) Psychiatric hospitalization within past 6 months;

(6) Unable to read, blind or deaf. Our previous study recruited only participants who were currently in treatment, but this study will include both participants who are currently in treatment, as well as those who are not in treatment. Intelligence Quotient (IQ) will be assessed with the North American Adult Reading Test (NART). 21-22 Subjects with a NART calculated IQ score of <90 will be excluded from the study.

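### No exclusion keeps participants of the lab's earlier tone-conditioning study out of the trial, so the premise that Control participants are naive to the tone is not secured

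*Combined protocol and SAP*

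**What the plan says.** All references are to the combined protocol and SAP.

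- **The premise.** Experimental Procedures, Testing Phase, sends the tone by text message to Control participants as well when they report high distress. The stated reason is to control for placebo effects, on the footing that these participants have not learned to associate the tone with anything. Conditions 1 and 2 describe the tone as new to the participant.
- **Recruitment.** Subject Recruitment and Compensation lists among its sources "Our IRB-approved participant registry (IRB# Pro00000853) in the CB RTP", and adds: "Subjects who have previously agreed to be in our database registry (IRB# Pro00000853) to be considered for research studies would be contacted".
- **People from other studies of the lab.** Measures and Tasks foresees them: "If the participant recently took part in another study at CBRTTP, he or she may not be required to complete all portions" of the diagnostic interview. The time limits given there (four weeks for SCID-I, six months for SCID-II) govern re-use of interview data. They are not a washout.
- **Exclusions.** Selection of Subjects lists seven: mania, psychotic symptoms, homelessness, suicidal ideation, recent psychiatric hospitalisation, inability to read, see or hear (with an IQ rule attached), and autistic traits. The earlier study is mentioned beside this list only to widen entry: "Our previous study recruited only participants who were currently in treatment, but this study will include both" treated and untreated people.
- **The earlier study.** Background & Significance reports that its auditory reminders of habituation lowered distress and arousal in the laboratory, and then: "Reminders delivered via mobile phones over one week also significantly reduced emotional distress compared to placebo sounds". Of the Habituation arm the plan says: "This comparison condition will most closely resemble the procedures of the previous study on generalizing emotion regulation".
- **Analysis.** Data Analysis & Statistical Considerations contains no record of, adjustment for, or stratification by earlier participation.

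**The concern.** Hypothesis 2 compares a tone that has been paired with falling arousal against the same tone without that pairing. The contrast is clean only if Control participants arrive without the pairing. The plan states this as a fact, but no entry rule makes it one.

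A person who received the active training in the earlier study and is now assigned to Control may already have had something close to Condition 2. When the phone plays the tone, that person may respond as a trained participant would. Each such person moves the Control mean towards the trained arms, and the Aim 2 difference between Mindful Breathing and Control shrinks. No analysis in the plan would detect this, because earlier participation is not recorded as a variable.

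**Working it through.** **Step 1. Is naivety secured?** Three routes could secure it: the recruitment sources, the entry criteria, or the analysis. The sources include the lab's registry. The criteria do not mention earlier participation. The analysis does not use it. The phone and online screening scripts are separate documents, but the plan describes the phone script as ruling out people who meet certain exclusion criteria, and earlier participation is not one of them. So the premise is unsecured.

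**Step 2. Could earlier participants qualify?** The plan gives a mean DERS of 117.6 (SD 17.95) for the earlier study's 208 eligible participants, and the entry threshold here is 90. Under a normal approximation the share at or above 90 is Φ((117.6 − 90)/17.95) = Φ(1.54) = 0.94. The threshold would not keep many out, although current DERS, IQ and autistic-trait rules still apply.

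**Step 3. Where would carry-over act?**
- *Training session (Aim 1).* Control hears no tone, so earlier tone learning is not cued there.
- *Testing phase (Aim 2).* Control hears the tone, so this is where it matters.
- *Mindful Breathing versus Habituation.* Earlier learning among Control participants does not touch this contrast.
- *Stressor.* Scripts are written afresh from events of the past two weeks, so only familiarity with the procedure can carry over, not script content.

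**Step 4. The plan's own power figure.** Inputs: f = 0.38, two-sided type I error 5%, N = 72 in three equal groups. One-way F test with 2 and 69 degrees of freedom and non-centrality λ = N f² = 72 × 0.38² = 10.40. Power is 81.3%, which agrees with the stated minimum of 80%.

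**Step 5. Illustration only.** The documents give neither the overlap nor the degree of carry-over. Assume that 10–30% of entrants come from the earlier study and that half of those were conditioned. Then a share c = 5–15% of Control is affected, which is 1.5 to 4.5 of the 30 people randomised to it. Assume also, as a worst case, that each responds exactly like a Mindful Breathing participant, with the within-group SD unchanged.

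With Mindful Breathing apart from two equal arms, d = 3f/√2 = 3 × 0.38/√2 = 0.806. The difference from Control becomes 0.806 × (1 − c). The three means become d, 0 and cd, so f becomes 0.38 × √(1 − c + c²).

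| c | difference from Control (SD) | f | three-group power, N = 72 |
|---|---|---|---|
| 0 | 0.806 | 0.380 | 81.3% |
| 5% | 0.766 | 0.371 | 79.3% |
| 15% | 0.685 | 0.355 | 75.5% |

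The answer depends on the assumed pattern. If Habituation instead equals Mindful Breathing and only Control stands apart, f becomes 0.38 × (1 − c), that is 0.361 to 0.323, and power 77.0% to 66.8%. In both patterns 0.38 is the effect planned for the main comparison of emotion-perception bias. It is not an estimate of the tone effect in Aim 2, for which the plan gives no effect size.

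**The case against.** The strongest reply is that the harm is conjectural, and much of it stands.

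- **The overlap has no source.** The plan says the lab has run over 980 participants since 2004. The earlier study's 208 are about 21% of these (208/980). If the registry mirrors that mix, a 10% overlap needs about 47% of entrants to come through the registry (0.10/0.212). A 30% overlap would need 141%, which is impossible. The registry is one of several recruitment routes, and nothing says how many earlier participants joined it.
- **The tone may differ.** If it does, carry-over requires generalisation from one sound to another.
- **Full transfer is a worst case.** The earlier study's results reported in the plan concern distress and arousal, not emotion perception.
- **Other remedies exist.** Using a different tone, or recording earlier participation, would answer part of the concern without excluding anyone.

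A reader might infer more than the documents support, in four ways:

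- *That every arm is compromised, or that stressor learning carries over.* The scripts are new, and the premise at issue concerns Control.
- *That the comparison is biased.* Randomisation balances earlier exposure on average, so the expectation is dilution, with chance imbalance possible at 24 to 30 per arm.
- *That people who heard placebo sounds earlier have learned to disregard tones.* Nothing in the documents supports this.
- *That the counts of 208 eligible and 169 enrolled measure a pool available to this trial.* They describe earlier work, and the 169 is not tied to a study number.

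None of this answers the gap itself: the plan states that Control participants are naive and has no rule that makes it so.

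**Conclusion.** The concern holds as a gap between a stated premise and the entry criteria. As written, a person conditioned in the earlier study can be contacted, found eligible and assigned to Control, where the plan counts that person as having no association with the tone. The expected effect is a weaker contrast between Mindful Breathing and Control, mainly in Aim 2.

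Its size cannot be derived, because the number affected and the identity of the tone are not stated. The Control-only illustration (81% power falling to 79–75% with one arm apart) rests on an assumed overlap, full carry-over and a borrowed effect size. It should not be read as an estimate of loss in this trial. The case for acting is that the premise matters to the design, the correction is cheap, and conditioning that people bring with them cannot be undone after enrolment.

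**What to change.** 1. Add to the exclusion criteria in Selection of Subjects: prior participation in Pro000035922, or in any study of the lab that paired a sound with emotion regulation. Confirm the study number, since Condition 2 prints it as Pro00035922.
2. Check each candidate against the rosters of those studies at the phone or online screen.
3. For anyone already enrolled, record earlier participation, and the arm if known, and add a sensitivity analysis of Aim 2 without these participants.
4. State whether the tone is the one used in the earlier study.

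The re-use of diagnostic interviews can continue for people from the lab's other studies. The change needs one criterion and a roster check, and no stated sample-size figure moves. The downside is a slightly smaller registry pool; the other recruitment routes are unaffected.
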